6.3.2 Day 7 Visit

All participants will return to the clinic for study drug dosing on Day 7(+2). Prior to the administration of the study drug, the participant will be evaluated clinically to assess the development of clinically significant conditions that may contraindicate dosing.

Note: To avoid unblinding on the dose administration worksheet, if a participant is under 50 kg, the volume of FCM or placebo administered should be calculated based on the participant's weight, e.g. a 45 kg participant will receive a 13.5 mL dose of FCM or placebo.

Group A participants the following will be performed:

- Verify amount of single FCM dose (15 mg/kg up to a maximum dose of 750 mg) (unblinded staff)
- Pre-administration, obtain heart rate, blood pressure, and body temperature (blinded staff)

- Administer FCM as a slow IV injection at the rate of approximately 2 mL /minute taking appropriate measures to ensure the participant and all blinded staff members remain blinded to the treatment being administered (unblinded staff).
- Document start and stop time of FCM administration and the total dose and volume administered (unblinded staff).
- Post-administration, obtain heart rate and blood pressure immediately after and 30 minutes after FCM administration (blinded staff). Participants will be discharged from the site by the Investigator or his or her designee only if there are no significant signs or symptoms 30 minutes after the administration is completed.
- Adverse event / serious adverse event assessment, including evaluation of potential endpoint events (see Section 10.2; blinded staff)
- Review concomitant medications

Group B participants the following will be performed:

- Pre-administration, obtain heart rate, blood pressure, and body temperature (blinded staff)
- Administer a 15 mL dose of placebo (normal saline) as a slow IV injection at the rate of approximately 2 mL /minute taking appropriate measures to ensure the participant and all blinded staff members remain blinded to the treatment being administered (unblinded staff).
 - Document start and stop time of placebo administration and the total volume administered (unblinded staff).
 - Post-administration, obtain heart rate and blood pressure immediately after and 30 minutes after placebo administration (blinded staff). Participants will be discharged from the site by the Investigator or his or her designee only if there are no significant signs or symptoms 30 minutes after the administration is completed.
 - Adverse event/serious adverse event assessment, including evaluation of potential endpoint events (see Section 10.2; blinded staff).
 - Review concomitant medications (blinded staff)

6.4 Follow-Up Phase

6.4.1 90 Day Follow-Up

Following the initial and all subsequent courses of study drug treatments each participant will be contacted in person or via telephone 90 \pm 14 days post the first treatment for that course (i.e. study Days 90 \pm 14, 270 \pm 14, 450 \pm 14, 630 \pm 14, 810 \pm 14, 990 \pm 14...EOS)

During these visits the following will be performed:

- Adverse event / serious adverse event assessment, including evaluation of potential clinical endpoint events (see Section 10.2). (blinded staff)

6.4.2 6 Month Laboratory Evaluation

Participants will receive an additional course of study medication every 180 (± 7) days. Within 4 to 20 days prior to these scheduled dosing visits, all participants will return to the clinic to obtain central lab hematology, chemistry, and iron indices laboratory tests. 1,25 (OH)₂ Vitamin D, 25 (OH) Vitamin D and PTH for participants of the hypophosphatemia sub-study. (Blood to be collected by blinded staff)

6.4.3 Additional Study Drug Dosing (Every 6 Months)

All participants will be dosed every 6 months. At each 6-month interval, a course of 2 doses of study drug will be administered as described above for Day 0 and Day 7 (Section 6.3). For group A, FCM will be administered if Hgb < 13.5 g/dL (females) or <15.0 g/dL (males) and serum ferritin <100 ng/mL or 100 to 300 ng/mL with TSAT <20%; observe carefully that placebo (normal saline) will be administered to participants in the FCM group who do not meet the above criteria. All group B participants will receive placebo (normal saline).

6.4.3.1 6 Month Dosing Visit #1 (Days 180 ± 7 , 360 ± 7 , 540 ± 7 , 720 ± 7 , 900 ± 7 , 1,080 ± 7 ...EOS)

On the first of the 2 dosing visits, the following will be performed by blinded study staff for all participants:

- Weight
- Urine or serum pregnancy test (women of childbearing potential only)
- Adverse event / serious adverse event assessment, including evaluation of potential endpoint events (see Section 10.2).
- Review concomitant medications
- Administer 6MWT per standardized procedure (at the 6 and 12 month visits).

Note: To avoid unblinding on the dose administration worksheet, if a participant is under 50 kg, the volume of FCM or placebo administered should be calculated based on the participant's weight, e.g. a 45 kg participant will receive a 13.5 mL dose of FCM or placebo.

For Group A participants the following will be performed:

- Verify if participant will receive FCM or placebo, based on the following criteria from recent labs (within 20 days). Participants will receive FCM if the Hgb <13.5 g/dL (females) or <15.0 g/dL (males) and serum ferritin <100 ng/mL or 100 to 300 ng/mL with TSAT <20%. If the participant does not meet these criteria, placebo (normal saline) will be administered. (unblinded staff)
- As appropriate based on criteria above, verify amount of single FCM dose (15 mg/kg up to a maximum dose of 750 mg) or placebo (15 mL). (unblinded staff)
- Pre-administration, obtain heart rate, blood pressure, and body temperature. (blinded staff)
- Administer FCM or placebo as a slow IV injection at the rate of approximately 2 mL /minute. Appropriate measures must be taken to ensure the participant and all blinded

staff members remain blinded to the treatment being administered (unblinded staff)

- Document start and stop time of IV administration, and the total dose and volume administered (unblinded staff)
- Post-administration of FCM, obtain heart rate and blood pressure immediately after and 30 minutes after FCM administration (blinded staff). Participants will be discharged from the site by the Investigator or his or her designee only if there are no significant signs or symptoms 30 minutes after the administration is completed.

For Group B participants the following will be performed:

- Pre-administration, obtain heart rate, blood pressure and body temperature. (blinded staff)
- Administer a 15 mL dose of placebo (normal saline) as a slow IV injection, at the rate of approximately 2 mL /minute. Taking appropriate measures to ensure the participant and all blinded staff members remain blinded to the treatment being administered (unblinded staff)
 - Document start and stop time of placebo administration and the total volume administered. (unblinded staff)
 - Post-administration of placebo, obtain heart rate and blood pressure immediately after and 30 minutes after placebo administration (blinded staff). Participants will be discharged from the site by the Investigator or his or her designee only if there are no significant signs or symptoms 30 minutes after the administration is completed.

6.4.3.2 Six Month Dosing Visit #2 (Days 187 \pm 7, 367 \pm 7, 547 \pm 7, 727 \pm 7, 907 \pm 7, 1,087 \pm 7...EOS)

The second of the 2 dosing visits should occur at Day 7 (\pm 2) after the first, with the following performed for all participants:

- Adverse event / serious adverse event assessment, including evaluation of potential endpoint events (see Section 10.2). (blinded staff), and review of concomitant medications (blinded staff).

Note: To avoid unblinding on the dose administration worksheet, if a participant is under 50 kg, the volume of FCM or placebo administered should be calculated based on the participant's weight, e.g. a 45 kg participant will receive a 13.5 mL dose of FCM or placebo.

For Group A participants the following will be performed:

- Verify amount of single FCM dose (15 mg/kg up to a maximum dose of 750 mg) or placebo (15 mL). Note: participant should receive the same product (FCM or placebo) as received at the first dose of this course of treatment. (unblinded staff)
- Pre-administration, obtain heart rate, blood pressure, and body temperature. (blinded staff)
- Administer FCM or placebo as a slow IV injection at the rate of approximately 2 mL

/minute. Taking appropriate measures to ensure the participant and all blinded staff members remain blinded to the treatment being administered (unblinded staff).

- Document start and stop time of IV administration and the total dose and volume administered. (unblinded staff)
- Post-administration, obtain heart rate and blood pressure immediately after and 30 minutes after FCM administration. (blinded staff). Participants will be discharged from the site by the Investigator or his or her designee only if there are no significant signs or symptoms 30 minutes after the administration is completed.

For Group B participants the following will be performed:

- Pre-administration, obtain heart rate, blood pressure, and body temperature (blinded staff).
- Administer a 15 mL dose of placebo (normal saline) as a slow IV injection, at the rate of approximately 2 mL /minute. Taking appropriate measures to ensure the participant and all blinded staff members remain blinded to the treatment being administered (unblinded staff)
 - Document start and stop time of placebo administration and the total volume administered. (unblinded staff).
 - Post-administration, obtain heart rate and blood pressure immediately after and 30 minutes after placebo administration. (blinded staff). Participants will be discharged from the site by the Investigator or his or her designee only if there are no significant signs or symptoms 30 minutes after the administration is completed.

6.5 End of Study Visits

End of study visits for all participants will be scheduled once the last participant has reached 12 months on study and at least 771 participants have experienced an event of cardiovascular death or hospitalization for heart failure. The participants should return to the clinic and the following will be performed by blinded study staff:

- Targeted physical exam
- Vital signs including BP and heart rate
- Blood samples for central lab hematology, chemistries, iron indices and NT-proBNP.
- Urine or serum pregnancy test (women of childbearing potential only)
- Review of concomitant medications
- Adverse event / serious adverse event assessment, including evaluation of potential endpoint events (see Section 10.2).

6.6 Laboratory Assessments

Serum samples for laboratory analyses must be obtained at all appropriate visits. The method of analysis of screening laboratory values will be by a central clinical laboratory. All visit laboratory samples will be analyzed by a central clinical laboratory. All laboratory testing will be provided to the investigator or his/her

medically qualified designee for review and assessment. Post dose iron indices and serum phosphorus results will be provided to the designated unblinded investigator for assessment. The laboratory assessments will be determined as listed in Section 3.3:

- Hematology: Hgb, Hct, RBC, WBC, MCV, MCH, MCHC, RDW, platelets, differential count, and reticulocyte count
- Chemistry: Sodium, potassium, chloride, BUN, creatinine, albumin, alkaline phosphatase, total bilirubin, GGT, AST, ALT, LDH, calcium, phosphorus, glucose, bicarbonate, and magnesium
- Iron indices: Serum iron, serum ferritin, total iron binding capacity (TIBC), and percentage serum transferrin saturation (TSAT)
- Other: 1,25 (OH)₂ Vitamin D, 25 (OH) Vitamin D and PTH, and NT-proBNP

7.0 ASSESSMENT OF SAFETY

7.1 Adverse Events

Any untoward medical event experienced by a participant during the course of this clinical trial, whether or not it is related to the investigational product, at any dose, is considered an adverse event (AE).

For any laboratory abnormality, the investigator, or his/her medically qualified designee, will make a judgment as to its clinical significance. If the laboratory value is outside the normal limits and is felt to represent a clinically significant worsening from the baseline value, it should be considered an adverse event. If the laboratory value is outside the normal range, but not an adverse event, the investigator should comment on the findings (i.e. “not clinically significant” or “unchanged from baseline”) in the source documentation [laboratory report].

Table 7.1.1 Grading of Adverse Event Severity

Grade	Adjective	Description
1	Mild	Does not interfere with the participant’s usual function
2	Moderate	Interferes to some extent with participant's usual function
3	Severe	Interferes significantly with participant's usual function
4	Life-threatening	Results in a threat to life or in an incapacitating disability
5	Death	Results in Death

Timing: Adverse events and serious adverse events will be reported, as described below in Section 7.2, from the time of randomization through the end of study. Adverse events for participants randomized and who terminate early will be reported for 30 days after the last treatment.

Timing: Adverse events and serious adverse events will be reported, as described below in Section 7.2, from the time of randomization through the end of study. Adverse events for participants randomized and who terminate the study early or permanently discontinue study drug (Section 4.5) will be reported for 30 days after the last treatment. All reported SAEs should be followed until no longer serious or return to baseline grade.

Relationship (Causality): The Investigator will be asked to document his/her opinion of the relationship of the event to the study drug* as follows:

- NONE There is *no* evidence of any causal relationship.
- UNLIKELY There is *little* evidence to suggest there is a causal relationship. There is *another reasonable explanation* for the event (e.g., the participant's clinical condition, other concomitant treatments).
- POSSIBLE There is *some* evidence to suggest a causal relationship (i.e. there is a reasonable possibility that the adverse experience may have been caused by the agent). However, the influence of *other factors may have contributed* to the event (e.g., the participant's clinical condition, other concomitant events).
- PROBABLE There *is evidence* to suggest a causal relationship, and the influence of other factors is *unlikely*.

* For the purposes of this trial, "study drug" is defined as:

FCM

OR

Placebo

7.2 Reporting of Adverse Events

For the purposes of this study, any AE that does not meet the protocol definition of a serious AE is considered non-serious.

All SAEs and only AEs leading to study drug discontinuation will be collected in this study. Non-serious AEs that do not lead to study drug discontinuation (Section 4.5) are not being collected in this study.

Adverse experiences will be elicited by nonspecific questions such as "Have you noticed any problems?" Participants will be encouraged to report adverse events at their onset.

Disease progression can be considered as a worsening of a patient's clinical condition attributable to the disease in the patient population for which the study medication is being studied. It may be an increase in the severity of the disease under study, and/or increases in the symptoms of the disease. These also include the events listed in Section 7.4, "Reporting of Events that May Require Adjudication."

The development of the following cardiovascular disease events will be recorded in the eCRF, however they should be considered as disease progression and will not be reported as an AE/SAE during the study unless determined to be clinical endpoints.

1. Supraventricular arrhythmia (e.g., atrial fibrillation) requiring urgent/emergent intervention
2. Ventricular arrhythmia (e.g., ventricular tachycardia or fibrillation) requiring urgent/emergent intervention including ICD shock
3. Renal failure requiring urgent/emergent intervention (e.g., initiation of dialysis)

These three events will be documented on a dedicated form in the eCRF and they will be reported to the DSMB. An analysis as well as summary data tables of these events will be provided in the safety section of the clinical study report which will also include a rationale for exclusion of these events from AE or SAE reporting. Data files containing information about the above events will be included in the Regulatory submission in addition to hyperlinks or other means to easily direct reviewers to the location of the data.

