5.3 IV Medication Precautions

When administering FCM or Placebo, the following precautions will be taken:

- The participant will be evaluated clinically prior to drug administration to assess the development of clinically significant conditions.
- The vials will be visually inspected for particulate matter and discoloration before use. If noted, the vial will not be used, and the Investigator or his designee will notify the sponsor or sponsor's designee for replacement of the study drug, and for direction on the return of the unused vial.
- Heart rate and blood pressure will be assessed pre-, immediately post, and 30 minutes post administration. Participants will be discharged from the site by the Investigator or his or her designee only if there are no significant signs or symptoms 30 minutes after the administration is completed.
- The participant will be monitored for at least 30 minutes for serious acute reactions as hypersensitivity or bioactive (labile) iron reactions to non-dextran IV iron products have rarely been reported. The reactions include: hypotension, loss of consciousness, bronchospasm with dyspnea, shortness of breath, and seizures.
 - In the event a serious acute reaction is seen, the site must have the capability to provide appropriate resuscitation measures. These may include IV NS, IV epinephrine, steroids, and/or antihistamines.

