7.3 Serious Adverse Events

Definition: An adverse event is classified as SERIOUS if it meets any one of the following criteria:

- **Death**
- **Life-Threatening:** The participant was at substantial risk of dying at the time of the adverse event or it is suspected that the use or continued use of the product would result in the participant's death.
- **Hospitalization (initial or prolonged):** Required admission to the hospital or prolongation of a hospital stay except events which are components of the primary or secondary endpoints which will be adjudicated by the CEC Committee as noted above.
- **Disability:** Resulted in a significant, persistent, or permanent change, impairment, damage or disruption in the participant's body function/structure, physical activities or quality of life.
- **Congenital Anomaly/Birth Defect.**
- **Important medical events:** Other medically important events that, in the opinion of the investigator, may jeopardize the participant or may require intervention to prevent one of the other outcomes listed above.

Suspected clinical endpoint events that may traditionally meet the definition of an SAE, will not be reported by the sites in this trial as an SAE, but will be reported as a suspected clinical endpoint. Those events will therefore not be reported to the sponsor's Drug Safety Surveillance department.

Certain events of interest (supraventricular arrhythmia, ventricular arrhythmia, and renal failure) that are related to heart failure (serious and non-serious) will be listed on the eCRF and not be reported by the site as an SAE.

These events will be monitored by the Data Safety Monitoring Board to ensure participant safety.

Additionally suspected clinical events that are reviewed by the CEC but do not meet the criteria of an endpoint event will then be reviewed by the safety surveillance team for possible unreported SAEs.

Reporting: Any SAE as defined by this protocol, starting with the time of randomization, that is to be reported (as outlined in the section above) must be reported immediately (by the end of the next business day) to American Regent, Inc. This occurs through entry into the eCRF by the local investigator/coordinator and completing the SAE module. In the event that the eCRF module is not available and paper forms have not been provided for use, the investigator will contact the Study Safety Monitor at:

American Regent, Inc.

████████████████████

██

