7.4 Reporting of Suspected Study Endpoint Events that May Require Adjudication

The following events, which are the components of the primary or secondary endpoints will be adjudicated by the Clinical Events Classification (CEC) Committee of the Duke Clinical Research Institute (DCRI) for both FCM and Placebo and will not require reporting to the sponsor as an SAE:

- Cardiovascular Death including:
 - Death due to Heart Failure
 - Death due to Acute Myocardial Infarction
 - Sudden Cardiac Death

- Death due to Stroke
- Death due to other cardiovascular causes
- Hospitalization for heart failure
- Non-Cardiovascular death
- Hospitalization for myocardial infarction
- Hospitalization for stroke
- Other Cardiovascular hospitalizations
- Urgent heart failure visits

Therefore, any event that may possibly constitute one of these endpoints will be evaluated by the CEC Committee by a procedure described in separate documentation. A description of the CEC Committee and the definitions of the above clinical endpoints may be found in Section 10.2.

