9.2 Investigator Responsibilities

By signing the Form FDA 1572 the Investigator agrees to:

1. Conduct the study in accordance with the protocol and only make changes after notifying the Sponsor, except when necessary to protect the safety, rights or welfare of participants.
2. Personally conduct or supervise the study (or investigation).
3. Inform any participants that the drug is being used for investigational purposes.
4. Ensure that the requirements relating to obtaining informed consent and IRB review and approval meet Federal guidelines, as stated in 21 CFR, parts 50 and 56.
5. Report to the Sponsor any adverse events that occur in the course of the study, in accordance with 21 CFR 312.64.
6. Have read and understood the Investigator's Brochure, including potential risks and side effects of the drug.
7. Ensure that all associates, colleagues and employees assisting in the conduct of the study are informed about their obligations in meeting the above commitments.
8. Maintain adequate and accurate records, in accordance with 21 CFR 312.62 and to make those records available for inspection with the Sponsor, their designated representative, the FDA or any agency authorized by law.
9. Ensure that an IRB that complies with the requirements of 21 CFR Part 56 will be responsible for initial and continuing review and approval of the clinical study.
10. Promptly report to the IRB and the Sponsor all changes in the research activity and all unanticipated problems involving risks to participants or others (including amendments and IND safety reports).
11. Not make any changes in the research study without approval, except when necessary to eliminate hazards to the participant/participants.
12. To comply with all other requirements regarding the obligations of the clinical investigators and all other pertinent requirements listed in 21 CFR Part 312.

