1.4. Symptoms and Signs of Hypophosphatemia

Although an FGF23-mediated decrease in serum phosphate after a single infusion of iron is usually transient, the risk of developing clinical symptoms and the actual clinical presentation is determined by the severity of hypophosphatemia and the time to recovery. Management of hypophosphatemia is within the judgment and discretion of the investigator.

Patients with hypophosphatemia typically report bone pain, general weakness, and asthenia [Okada, 1982; Schouten, 2009b; Mani, 2010; Shiraki, 1986; Sato, 1998; Suzuki, 1998; Konjiki, 1994; Shimizu, 2009; Yamamoto, 2013; Moore, 2013; Blazevic, 2014; Fierz, 2014; Vandemergel, 2014; Barea Mendoza, 2014; Poursac, 2015; Sangros Sahun, 2016]. In severe cases, proximal myopathy that also affects the diaphragm and rhabdomyolysis have been reported. The latter can also affect the heart or cause cardiomyopathy or cardiac arrhythmias [Bacchetta, 2012]. Rare manifestations include hemolysis, encephalopathy, seizures [Haglin, 2016]. The type of clinical manifestation expression is also dependent on the age at onset and the duration of hypophosphatemia. Young patients with long-standing hypophosphatemia typically present with growth retardation, delayed dentation and rickets [Elder, 2014]. In adults with hypophosphatemia persisting for several months, long-term complications such as osteomalacia can occur (Fig.2) [Gonciulea, 2017]. Presentation of osteomalacia can include bone pain, fractures, and pseudofractures, which may be difficult to diagnose on conventional X-ray.

Radiological findings are a coarse trabecular structure, and a loss of secondary trabeculae [Phan, 2016]. Low trauma fractures affecting the ribs or scapular "stress-" fractures of the lumbar spine, pelvic structures, and long bones such as femur, tibia, or metatarsal are also common complications of osteomalacia. More sensitive diagnostic tests to identify looser zones, known as 'pseudofractures,' include computed tomography, magnetic resonance imaging, and bone scintigraphy. Bone biopsy showing increased ratio of osteoid to bone surface and reduced tetracycline labeling remains the gold standard for diagnosis, but is rarely performed due to its invasiveness. Although there is

no specific laboratory test for osteomalacia, mildly elevated total and bone-specific alkaline phosphatase in plasma have been repeatedly reported in the context of iron-induced hypophosphatemia [Phan, 2016].

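### Protocol sections 7.2 to 7.4 take all deaths, CV hospitalizations, urgent HF visits and three urgent arrhythmia/renal events off the SAE route, with no stated exception for suspected drug causation

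*Combined protocol and SAP*

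**What the plan says.** All references are to protocol version 3.0 unless stated otherwise.

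- **Section 7.2** lists three events needing urgent or emergent intervention: supraventricular arrhythmia, ventricular arrhythmia and renal failure. It says "they should be considered as disease progression and will not be reported as an AE/SAE during the study unless determined to be clinical endpoints". Their alternative route is given next: "These three events will be documented on a dedicated form in the eCRF and they will be reported to the DSMB".
- **Section 7.3** says suspected endpoint events "will not be reported by the sites in this trial as an SAE, but will be reported as a suspected clinical endpoint", and that they therefore do not go to the sponsor's Drug Safety Surveillance department. For the same three arrhythmia/renal events it speaks of those "that are related to heart failure (serious and non-serious) will be listed on the eCRF and not be reported by the site as an SAE". Events that the Clinical Events Classification (CEC) Committee reviews and does not confirm as endpoints go to the safety surveillance team, to look for unreported SAEs.
- **Section 7.4** lists cardiovascular death, non-cardiovascular death, hospitalization for heart failure, MI, stroke or other cardiovascular cause, and urgent heart failure visits. These "will not require reporting to the sponsor as an SAE".
- **Section 9.2, item 5**, has the investigator agree to this: "Report to the Sponsor any adverse events that occur in the course of the study, in accordance with 21 CFR 312.64".

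The documents also describe how the drug could produce such events. Section 5.3 on acute reactions says: "The reactions include: hypotension, loss of consciousness, bronchospasm with dyspnea, shortness of breath, and seizures". Appendix 1, section 1.4, says of rhabdomyolysis in severe hypophosphatemia: "The latter can also affect the heart or cause cardiomyopathy or cardiac arrhythmias".

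**The concern.** Exempting adjudicated endpoints from SAE reporting is a reasonable choice in an outcome trial in heart failure, where deaths and admissions are expected and expedited reports of each would add noise. The weakness is that the exemption has no condition on cause. An investigator who believes that a death or a cardiovascular admission was caused by the injection finds nothing in section 7 that sends it to the sponsor's drug safety group by the end of the next business day. It goes to the CEC, which classifies it, and to the DSMB, which reviews safety data at least every six months or ad hoc (sections 8.10 and 10.3).

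At stake is how quickly a rare serious drug effect is recognised in a trial of about 3,014 participants with repeat dosing every six months. A handful of such events would be hard to see in counts of heart failure deaths and admissions.

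**Working it through.** No figure in the plan needs reproducing. The check is a comparison of passages, plus one calculation of scale.

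**1. Is there an exception for suspected causation?** Sections 7.1 to 7.4 were read for one. Section 7.1 asks the investigator for an opinion on relationship to study drug, but the answer changes no reporting route. Sections 7.2, 7.3 and 7.4 state none.

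**2. Can the second look in section 7.3 catch a death?** It applies only to events that do not meet an endpoint definition. Section 10.2.1 classifies every death as cardiovascular or non-cardiovascular, section 10.2.1.8 presumes an undetermined death to be cardiovascular, and section 7.4 lists both classes. So no death fails adjudication, and none reaches the safety team this way.

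**3. Would adjudication show the cause?** Non-cardiovascular deaths are not further adjudicated (10.2.1) or subclassified (10.2.1.7). Admission for arrhythmia is a named example of other cardiovascular hospitalization, which the CEC does not subclassify (10.2.2.4).

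**4. Is an infusion or hypersensitivity reaction exempt?** No. It is on neither the 7.2 list nor the 7.4 list, and it can meet the life-threatening or important-medical-event criteria of 7.3. The undefined case is one event that is both a reaction and an endpoint, such as a reaction that ends in death.

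**5. Do the sections agree?**

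| Topic | One passage | Another passage |
|---|---|---|
| Endpoints as AE/SAE | 7.2: the closing condition implies that events found to be endpoints are reported as AE/SAE | 7.3 and 7.4: endpoints are not reported as SAEs |
| Arrhythmia/renal exclusion | 7.2: the list has no limit to heart-failure-related events | 7.3: limited to heart-failure-related events |
| Death | 7.3: Death is an SAE criterion with no endpoint exception, though Hospitalization has one | 7.4: all deaths exempt |
| General duty | 9.2 item 5: report any adverse event | 7.2 to 7.4: the exemptions |

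SAP version 1.3, section 6.1, shows the same unsettled point. It does not regard outcome events as SAEs for the safety analysis, yet it plans a summary of treatment-emergent SAEs with a fatal outcome.

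**6. Scale of the exempt death route.** Inputs from protocol section 8.8: 1,507 per arm, with one-year deaths of 8% (control) and 6.8% (treatment).

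- Control: 1,507 × 0.08 = 120.6
- Treatment: 1,507 × 0.068 = 102.5
- Total: about 223 first-year deaths

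This counts all expected deaths, more than half of them on placebo. It shows how much traffic the route carries, not how many deaths would be suspected as drug-related. The documents give no rate for the latter, and section 5.3 calls serious acute reactions rarely reported.

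**The case against.** The strongest reply is that the plan leaves several routes open.

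- Infusion and hypersensitivity reactions remain reportable, and version 3.0 no longer carries the exemption for labelled serious drug effects found in section 7.3 of the original protocol. SAP 6.1 plans summaries of anaphylactic and infusion reactions. This stands. A reader might infer that a fatal infusion reaction can never reach sponsor safety, and the text does not support that: a site could report the reaction as life-threatening. What is missing is an instruction to do so when the same event is an endpoint.
- A reader might also infer that arrhythmia and renal failure are excluded whatever their suspected cause. Section 7.3 limits the exclusion to heart-failure-related events, and 7.2 describes disease progression as worsening attributable to the disease. This stands as a conflict to resolve, because the 7.2 list itself carries no such limit. Even on the 7.3 reading, an arrhythmia that leads to cardiovascular admission falls under 7.4.
- A further tempting inference is that endpoint events get no causality assessment. The endpoint form and the arrhythmia/renal form are not in the documents, and 7.1 does not expressly exempt endpoints, so this cannot be claimed.
- The DSMB monitors these events and can meet ad hoc, and 7.2 promises analysis, a rationale and data files for regulators on the three events. These safeguards are real, but none sets a next-business-day report to the sponsor.
- An exception triggered by suspicion may miss a phosphate-related arrhythmia. Blinded staff do not see post-treatment phosphorus (5.6), and the main-study schedule has no chemistry between Day 0 and Days 160–176 (3.3). This also stands and limits what the fix can achieve.

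**Conclusion.** The point holds as a gap and a set of contradictions in the live reporting rules. As written, a death or cardiovascular admission that the investigator suspects was caused by study drug is kept off the next-business-day route to the sponsor as an SAE. For deaths, the safety team's second look cannot correct this. The handling of a single event that is both a drug reaction and an endpoint is undefined, and sections 7.2, 7.3 and 7.4 disagree on endpoints, on the arrhythmia/renal exclusion and on death as an SAE criterion.

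The number of events affected is unknown and probably small. The figure of about 223 deaths is only the size of the exempt route on the planning rates. The conclusion rests on the text of protocol version 3.0; the CEC and DSMB charters and the case report forms, which are not in the documents, might narrow the gap. Quick recognition of a serious drug effect should not depend on that, so this deserves an amendment.

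**What to change.** 1. Add one exception to sections 7.2, 7.3 and 7.4. Any suspected endpoint, arrhythmia or renal-failure event that the investigator considers possibly or probably related to study drug, or that starts during injection or the 30-minute observation period, is **also** reported as an SAE by the existing next-business-day route. CEC adjudication is unchanged.
2. Make sure the existing causality question from 7.1 is on the endpoint form and on the dedicated arrhythmia/renal form.
3. Reconcile the sections. Delete the closing condition about clinical endpoints from the 7.2 sentence, align 7.2 and 7.3 on whether the arrhythmia/renal exclusion is limited to heart-failure-related events, and state in 7.3 how its Death criterion stands beside the 7.4 exemption.

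The cost is a short amendment, at most one field on each of two existing forms, and a small number of events reported twice. The efficacy analysis is unaffected. The change will not detect a phosphate-related arrhythmia that nobody suspects.
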